#### **7.1.7. Adverse Events of Special Interest**

Events of interest will be identified by the use of either SMQs or MSTs. However, should additional cases not detected by the predefined search term listings be identified during the clinical review process, these cases will be reported by the respective category.

##### **7.1.7.1. Adjudication Committee for MACE**

An independent cardiovascular safety endpoint adjudication committee (CVEAC) will be formed to periodically review and adjudicate all potential major cardiovascular adverse events (MACE). MACE is defined as cardiovascular death, nonfatal myocardial infarction and nonfatal stroke.

To identify the MACE, the following potential cases identified using MedDRA search listing (MST) searches will be adjudicated:

- All deaths
- Cardiovascular events (meeting serious criteria)
- Myocardial infarction
- Hospitalization for unstable angina
- Transient ischemic attack
- Stroke
- Hospitalization for cardiac failure
- Percutaneous coronary intervention

The CVEAC will review those potential MACE and related clinical data to determine whether a MACE has developed. The CVEAC's role and responsibilities and the data to be provided to the CVEAC are described in a mutually agreed upon CVEAC charter. The CVEAC charter defines the CVEAC membership, adjudication process, meeting logistics, and meeting frequency. The number and percentage of subjects with positively adjudicated MACE will be summarized by treatment group using the PT term.

A by-subject listing for all patients who have a potential MACE or a positively adjudicated MACE at any time will be provided.

#### 7.1.7.2. Other Adverse Events of Special Interest

In addition to general safety parameters and MACE, safety information on other adverse events of special interest (AESIs) will also be analyzed. AESIs will be identified by either laboratory results, standardized MedDRA queries (SMQs), or sponsor defined MSTs, or a combination of these methods as indicated below.

- All infections (defined as all PTs in the Infections and Infestations SOC)
- Serious infections (defined as all PTs in the Infections and Infestations SOC that are SAEs)
- Infections of special interest as defined below (identified by using MST)
  - a) Herpes zoster
  - b) Active tuberculosis
  - c) Opportunistic infections
  - d) Hepatitis B or C infections

- Deep vein thrombosis (DVT) and pulmonary embolism (PE) (identified by using MST)
- Malignancy (including lymphoma; not including nonmelanoma skin cancer) (identified by using MST)
- Nonmelanoma skin cancer (identified by MST)
- GI (Gastrointestinal) perforations (identified by MST)

The number and percentage of subjects with aforementioned events of special interest will be provided by the PT term for each AE of special interests.

A by-subject listing for all subjects having AE of special interests at any time will be provided for each AE of special interest.

## **7.2. Laboratory Evaluations**

Laboratory data collected during the study will be analyzed and summarized using both quantitative and qualitative methods. Summaries of laboratory data will be provided for the Safety Analysis Set and will include data collected up to the last dose of any study drug plus 30 days for subjects who have permanently discontinued study drug, or all available data at the time of the database snapshot for subjects who were ongoing at the time of an interim analysis. The analysis will be based on values reported in conventional units. When values are below the LOQ, they will be listed as such, and the closest imputed value will be used for the purpose of calculating summary statistics as specified in Section 3.7.

A by-subject listing for laboratory test results will be provided by subject ID number and visit in chronological order for hematology, serum chemistry, and urinalysis separately. Values falling outside of the relevant reference range and/or having a severity grade of 1 or higher on the CTCAE severity grade will be flagged in the data listings, as appropriate.

No formal statistical testing is planned.

### **7.2.1. Summaries of Numeric Laboratory Results**

Descriptive statistics of Baseline values, values at each postbaseline visit and change from Baseline at each postbaseline visit will be provided by treatment group for the following laboratory tests:

- Hematology
  - Hematocrit
  - Hemoglobin
  - Platelet count
  - Red blood cell count

- Mean corpuscular volume
- White blood cell (WBC) count
- Lymphocytes
- Monocytes
- Neutrophils
- Eosinophils
- Basophils
- Chemistry
  - Alanine aminotransferase (ALT)
  - Aspartate aminotransferase (AST)
  - Alkaline phosphatase (ALP)
  - Total bilirubin
  - Serum creatinine
  - Creatinine clearance by Cockcroft-Gault formula
  - Creatinine phosphokinase (CPK)
  - Glucose
- Lipid
  - Triglycerides
  - Total cholesterol
  - HDL
  - LDL
  - LDL/HDL ratio

A baseline laboratory value will be defined as the last measurement obtained on or prior to the date/time of first dose of any study drug. Change from baseline to a postbaseline visit will be defined as the visit value minus the baseline value. The mean, median, Q1, Q3, minimum, and maximum values will be displayed to the reported number of digits; SD values will be displayed to the reported number of digits plus 1.

Median (Q1, Q3) of the observed values for the laboratory tests specified above will be plotted using a line plot by treatment group and visit.

In the case of multiple values in an analysis window, data will be selected for analysis as described in Section 3.8.3.

## **7.2.2. Graded Laboratory Value**

The CTCAE Version 4.03 (with one modification specified in protocol) will be used to assign toxicity grades (0 to 4) to laboratory results for analysis. Grade 0 includes all values that do not meet the criteria for an abnormality of at least Grade 1. For laboratory tests with criteria for both increased and decreased levels, analyses for each direction (ie, increased, decreased) will be presented separately.

### **7.2.2.1. Treatment-Emergent Laboratory Abnormalities**

Treatment-emergent laboratory abnormalities are defined as values that increase at least 1 toxicity grade from baseline at any postbaseline time point, up to and including the date of last dose of any study drug plus 30 days for subjects who permanently discontinued study drug, or the last available date in the database snapshot for subjects who were still on treatment at the time of an interim analysis.

If the relevant baseline laboratory value is missing, any abnormality of at least Grade 1 observed within the time frame specified above will be considered treatment emergent.

### **7.2.2.2. Treatment-Emergent Marked Laboratory Abnormalities**

Treatment-emergent marked laboratory abnormalities are defined as values that increase from baseline by at least 3 toxicity grades at any postbaseline time point, up to and including the date of the last dose of any study drug plus 30 days for subjects who permanently discontinued study drug or the last available date in the database snapshot for subjects who were still on treatment at the time of an interim analysis.

If the relevant baseline laboratory value is missing, any Grade 3 or higher values observed within the timeframe specified above will be considered treatment-emergent marked abnormalities.

### **7.2.2.3. Summaries of Laboratory Abnormalities**

Laboratory data that are categorical will be summarized using the number and percentage of subjects in the study with the given response at baseline and each scheduled postbaseline visit.

The following summaries (number and percentage of subjects) for treatment-emergent laboratory abnormalities will be provided by laboratory test and treatment group; subjects will be categorized according to the most severe postbaseline abnormality grade for a given laboratory test:

- Graded laboratory abnormalities

- Grade 3 or higher laboratory abnormalities
- Marked laboratory abnormalities

For all summaries of laboratory abnormalities, the denominator is the number of subjects with nonmissing postbaseline values up to 30 days after last dosing date.

A by-subject listing of treatment-emergent Grade 3 or higher laboratory abnormalities and marked laboratory abnormalities will be provided separately by subject ID number and visit in chronological order. These listings will include all test results that were collected throughout the study for the laboratory test of interest, with all applicable severity grades or abnormal flags displayed.

### **7.2.3. Laboratory Evaluations of Special Interest**

#### **7.2.3.1. Liver-Related Laboratory Evaluations**

Liver-related abnormalities after initial study drug dosing will be examined and summarized using the number and percentage of subjects who were reported to have the following laboratory test values for postbaseline measurements:

- AST: (a) > 3 times of the upper limit of reference range (ULN); (b) > 5 x ULN; (c) > 10 x ULN; (d) > 20 x ULN
- ALT: (a) > 3 x ULN; (b) > 5 x ULN; (c) > 10 x ULN; (d) > 20 x ULN
- AST or ALT > 3 x ULN and total bilirubin > 2 x ULN

The summary will include data from all postbaseline visits up to 30 days after the last dose of any study drug. For individual laboratory tests, subjects will be counted once based on the most severe postbaseline values. For both the composite endpoints of AST or ALT and total bilirubin, subjects will be counted once when the criteria are met at the same postbaseline visit date. The denominator is the number of subjects in the Safety Analysis Set who have nonmissing postbaseline values of all relevant tests at the same postbaseline visit date. A listing of subjects who met at least 1 of the above criteria will be provided.

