- Subject use of prohibited concurrent therapy *may* trigger study drug discontinuation; consultation should be made with the Gilead medical monitor.
- Laboratory criteria:

After becoming aware of any of the below described abnormal laboratory changes occurring at any one time, an unscheduled visit (ie sequential visit) should occur to retest within 3 to 7 days (except creatinine, which should be retested 7-14 days apart).

— 2 sequential neutrophil counts <750 neutrophils/mm³ (SI: $<0.75 \times 10^9$ cells/L) after dose adjustment of MTX/PTM (Section 5.3.4)

- 2 sequential platelet counts $<75,000$ platelets/mm³ (SI: $<75.0 \times 10^9$ cells/L) after dose adjustment of MTX/PTM (Section 5.3.4)
- 2 sequential AST or ALT elevations $>3 \times \text{ULN}$ and ≥ 1 total bilirubin value $>2 \times \text{ULN}$ or accompanied by symptoms consistent with hepatic injury¹ after dose adjustment of MTX/PTM (Section 5.3.4)
- 2 sequential AST or ALT elevations $>5 \times \text{ULN}$ after dose adjustment of MTX/PTM (Section 5.3.4)
- 2 sequential values for estimated creatinine clearance <35 mL/min based on the Cockcroft Gault formula

Subjects who permanently discontinue study medication for any reason are to receive standard of care treatment for their RA as determined by the investigator, and those subjects should be encouraged to continue study visits and procedures, if deemed medically appropriate by the investigator. Subjects who permanently discontinue study medication for pregnancy should not continue in the study; if there are any questions regarding permanent discontinuation, these should be discussed with the Sponsor.

Subjects withdrawing from the study should complete ET and Post Treatment Week 4 visits. Subjects are free to withdraw from the study at any time without providing reason(s) for withdrawal and without prejudice to further treatment. The reason(s) for withdrawal will be documented in the electronic case report form (eCRF).

Reasonable efforts will be made to contact subjects who are lost to follow-up. These must be documented in the subject's file.

The sponsor has the right to terminate the study at any time in case of safety concerns or if special circumstances concerning the study medication or the company itself occur, making further treatment of subjects impossible. In this event, the investigator(s) and relevant authorities will be informed of the reason for study termination.

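### The combined AST/ALT-and-bilirubin row in SAP 7.2.3.1 counts same-date elevations only, so a subject with the same elevations on different dates is absent from that row

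*SAP*

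**What the plan says.** SAP 7.2.3.1 (Liver-Related Laboratory Evaluations) lists three kinds of entry:

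- AST alone and ALT alone, each above 3, 5, 10 and 20 x ULN. The counting rule is: "For individual laboratory tests, subjects will be counted once based on the most severe postbaseline values".
- One combined criterion: "AST or ALT > 3 x ULN and total bilirubin > 2 x ULN". Its counting rule is: "subjects will be counted once when the criteria are met at the same postbaseline visit date". Its denominator is restricted to Safety Analysis Set subjects "who have nonmissing postbaseline values of all relevant tests at the same postbaseline visit date".
- A by-subject listing: "A listing of subjects who met at least 1 of the above criteria will be provided".

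The data window is the same throughout: "The summary will include data from all postbaseline visits up to 30 days after the last dose of any study drug".

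Protocol 3.5.2 (laboratory criteria for permanent discontinuation) contains a hepatic criterion that begins "2 sequential AST or ALT elevations" above 3 x ULN. It adds either at least one total bilirubin value above 2 x ULN or symptoms of hepatic injury, and it applies after MTX/PTM dose adjustment. A separate criterion covers two sequential values above 5 x ULN. For most of the listed abnormalities, "an unscheduled visit (ie sequential visit) should occur to retest within 3 to 7 days". Protocol 6.7.3 asks for prompt retesting of the parameters affected and does not require the whole chemistry panel to be redrawn.

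**The concern.** The SAP row and the bilirubin part of the protocol criterion share their thresholds but not their timing. The protocol criterion needs at least two transaminase dates and leaves the date of the bilirubin value open. The SAP row needs both elevations on a single date. If bilirubin crosses 2 x ULN only after the transaminases have fallen back, or before they have risen, the row records nothing.

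This matters because the row is the only planned summary that separates, by treatment group, subjects with both elevations from those with a transaminase rise alone. Protocol 5.3.4 names confirmed transaminase elevation as a possible sign of MTX intolerance, so the single-test rows will mix the two kinds of subject. The adverse events of special interest in SAP 7.1.7.2 have no hepatic-injury category, and the graded abnormality summaries in SAP 7.2.2.3 work one test at a time. An arm could show zero in the combined row while containing a subject who met the AST/ALT-plus-bilirubin part of Protocol 3.5.2.

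**Working it through.** The plan gives no figure to reproduce here, so the check applies the two definitions to the same data. All laboratory values and days below are hypothetical, in multiples of ULN. AST is taken as never above 3, values fall inside the data window, and any dose adjustment has already taken place.

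**Definitions**

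- Protocol part (3.5.2): two consecutive ALT values > 3, and at least one bilirubin value > 2 on any date.
- SAP combined row (7.2.3.1): at least one date with ALT > 3 and bilirubin > 2 together.
- SAP single-test row (7.2.3.1): at least one ALT value > 3.

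**Example subjects**

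| Subject | Day 57 ALT / bilirubin | Day 62 | Day 67 | Protocol part | Combined row | ALT > 3 row and listing |
|---|---|---|---|---|---|---|
| Bilirubin later | 4.0 / 1.4 | 3.5 / 1.8 | 2.6 / 2.3 | met | 0 | 1 |
| Bilirubin first | 2.5 / 2.2 | 3.6 / not drawn | 3.4 / not drawn | met | 0 | 1 |

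Both subjects have ALT and bilirubin together on at least one date. They are therefore in the combined row's denominator and count as non-events.

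**All patterns on a small grid**

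Take three visits, ALT in {1, 2.5, 4, 6} and bilirubin in {missing, 1, 2.5}. Write H for ALT > 3 (two grid values) and L for ALT at or below 3 (two grid values).

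1. Two consecutive H values occur in HHH, HHL and LHH. ALT patterns: 3 x 2 x 2 x 2 = 24.
2. Bilirubin patterns with at least one value > 2: 27 - 8 = 19.
3. Patterns meeting the protocol part: 24 x 19 = 456.
4. Missed by the combined row: bilirubin > 2 occurs only at the L visit. HHL gives 8 x (2 x 2 x 1) = 32 and LHH gives 32, so 64 in total.
5. Missed by the ALT > 3 row and the listing: 0, because every qualifying pattern contains an H visit.

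If bilirubin is drawn at every visit, the same count gives 24 x (8 - 1) = 168 qualifying patterns, with 8 + 8 = 16 missed by the combined row. The gap therefore does not depend on partial retests.

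These are counts of patterns. They show that the gap exists and runs in both directions (32 bilirubin-later, 32 bilirubin-first). They are not expected frequencies.

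**Size per missed subject**

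With planned arms of 400 and 200, and assuming every subject is in the denominator, one uncounted subject is 1/400 = 0.25% or 1/200 = 0.5%.

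**The case against.** The strongest reply is that nothing is hidden. A reader might infer that a subject stopped under the protocol's hepatic criterion could vanish from the liver table. The documents do not support that. The criterion requires two AST/ALT values above 3 x ULN, so any such subject inside the data window is counted in a single-test row and appears in the listing. Other outputs would also show the case: the chronological chemistry listing (SAP 7.2), the table and listing of adverse events leading to discontinuation of study drug (SAP 7.1.6.1), and the listing of reasons for discontinuation (SAP 4.1). This part of the reply stands in full.

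A reader might also infer that the SAP contradicts the protocol. It does not. The protocol prescribes no combined liver tabulation, and the SAP never says that its row reproduces the stopping criterion. Nor does the protocol say that the elevations are expected on different dates; it only leaves the timing open. AST, ALT and bilirubin belong to one chemistry panel (Protocol Appendix 6), drawn at each scheduled visit, so many cases would be captured on a shared date.

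Subjects stopped on symptoms, or on values above 5 x ULN, whose bilirubin stays normal are also outside the combined row. That follows from the bilirubin threshold and not from the same-date clause, so it is not part of this point.

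What the reply does not answer is the missing by-arm count. The listing picks these subjects up through their transaminase values, and SAP 7.2.3.1 does not say that it will mark a bilirubin elevation on another date.

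**Conclusion.** The point holds for the combined row only. A subject meeting the AST/ALT-plus-bilirubin part of Protocol 3.5.2 can be absent from that row when the two elevations fall on different dates, while remaining visible in the single-test rows and the listing. It is a gap in a reporting definition and a worthwhile improvement, neither an error nor an inconsistency between the documents.

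The number of affected subjects is unknown because the documents give no liver event rates; it may be zero. The conclusion rests only on the wording of the two sections. The size per case, 0.25 or 0.5 percentage points, assumes planned arm sizes with all subjects evaluable. Because a combined elevation is likely to be uncommon (an assumption), even one such case could change how the row reads.

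**What to change.** In SAP 7.2.3.1:

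1. Keep the same-date row as it is.
2. Add a second row: subjects with any AST or ALT > 3 x ULN and any total bilirubin > 2 x ULN postbaseline, in either order, up to 30 days after the last dose of any study drug. If a limit on the gap between the two tests is preferred, prespecify it and apply it in both directions. A window that only looks forward from the transaminase value would still miss the bilirubin-first patterns.
3. For the new row, use as denominator the subjects with at least one postbaseline value of each test.
4. Flag these subjects in the existing listing, with the dates of both elevations.
5. Tidy the sentence that refers to more than one composite endpoint, since only one is listed.

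The cost is a few lines of SAP text and one derived flag from data already collected. The downside is that a few unrelated pairs may be counted; the dates in the listing would show them. The change affects reporting only and implies nothing about the stopping criteria in Protocol 3.5.2.

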#### **7.2.3.2. Complete Blood Count-Related Laboratory Evaluations**

Complete blood count (CBC)-related abnormalities such as anemia, leucopenia, neutropenia, lymphopenia, and thrombocytopenia after initial study drug dosing will be examined and summarized using the number and percentage of subjects who were reported to have the following laboratory test values for postbaseline measurements:

- Hemoglobin: (a) any postbaseline worsening CTCAE grade from baseline; (b) baseline value of less than Grade 3 and increase to Grade 3 or higher at worst postbaseline; (c) baseline value of less than Grade 3 and increase to Grade 4 or higher at worst postbaseline

- WBC count: (a) any postbaseline worsening CTCAE grade from baseline; (b) baseline value of less than Grade 3 and increase to Grade 3 or higher at worst postbaseline; (c) baseline value of less than Grade 3 and increase to Grade 4 or higher at worst postbaseline
- Absolute neutrophil count: (a) any postbaseline worsening CTCAE grade from baseline; (b) baseline value of less than Grade 3 and increase to Grade 3 or higher at worst postbaseline; (c) baseline value of less than Grade 3 and increase to Grade 4 or higher at worst postbaseline
- Lymphocyte count: (a) any postbaseline worsening CTCAE grade from baseline; (b) baseline value of less than Grade 3 and increase to Grade 3 or higher at worst postbaseline; (c) baseline value of less than Grade 3 and increase to Grade 4 or higher at worst postbaseline
- Platelet count: (a) any postbaseline worsening CTCAE grade from baseline; (b) baseline value of less than Grade 3 and increase to Grade 3 or higher at worst postbaseline; (c) baseline value of less than Grade 3 and increase to Grade 4 or higher at worst postbaseline

The summary will include data from all postbaseline visits up to 30 days after the last dose of any study drug.

### **7.3. Body Weight and Vital Signs**

Descriptive statistics will be provided by treatment group for body weight, BMI and vital signs (systolic and diastolic blood pressures [mmHg], pulse [beats/min] ) as follows:

- Baseline value
- Values at each postbaseline visit
- Change from baseline at each postbaseline visit

A baseline value will be defined as the last available value collected on or prior to the date/time of first dose of any study drug. Change from baseline to a postbaseline visit will be defined as the postbaseline value minus the baseline value. Body weight and vital signs measured at unscheduled visits will be included for the baseline value selection.

In the case of multiple values in an analysis window, data will be selected for analysis as described in Section 3.8.3. No formal statistical testing is planned.

A by-subject listing of vital signs (systolic and diastolic blood pressure [mmHg], pulse [beats/min], respiration [breaths/min], and body temperature [°C]) will be provided by subject ID number and visit in chronological order. In the same manner, a by-subject listing of body weight, height, and BMI will be provided separately

## **7.4. Prior and Concomitant Medications**

Medications collected at screening and during the study will be coded using the World Health Organization (WHO) Drug dictionary version BSEP17

All the analyses in this section will be performed for general prior /concomitant medications and RA-specific prior/concomitant medications separately, unless otherwise specified.

